6.3.2. Repeated or Unscheduled Assessments of Safety Parameters

If a participant has repeated assessments before the administration of treatment, unless otherwise stated, the results from the latest non-missing assessment made prior to the start of the study treatment will be used as baseline. If end-of-study assessments are repeated or if unscheduled visits occur, the last non-missing postbaseline assessment will be used as the end-of-study assessment for generating summary statistics. However, all postbaseline assessments will be used for safety evaluation, and all assessments will be presented in the data listings.

6.3.3. Missing Date of the Last Dose of Study Intervention

For participants who did not receive the LUMIGAN 0.01% at the Week 8 Sleep Lab visit or missed at the Week 8 Sleep Lab visit, the date will be imputed with the last non-missing date of treatment self-administration prior to Week 8 Sleep Lab visit.

6.3.4. Missing Severity Assessment for Adverse Events

If severity is missing for an AE that started before the date of study treatment, severity of mild will be assigned. If severity is missing for an AE that started on or after the date of study treatment, severity of severe will be assigned. The imputed values for severity assessment will be used for the incidence summaries; the values will be shown as missing in the data listings.

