### **8.3.3. Follow Up of Adverse Events and Serious Adverse Events**

After the initial AE/SAE report, the investigator is required to proactively follow each participant at subsequent visits/contacts. All AEs/SAEs will be followed until resolution, stabilization, the event is otherwise explained, or the participant is lost to follow-up (as defined in Section 7.3).

The investigator is obligated to perform or arrange for the conduct of supplemental measurements and/or evaluations as medically indicated or as requested by the sponsor or designee to elucidate the nature and/or causality of the AE or SAE as fully as possible. This may include additional laboratory tests or investigations, histopathological examinations, or consultation with other health care professionals.

If a participant dies during participation in the study or during a recognized follow-up period, the investigator will provide Allergan with a copy of any postmortem findings including histopathology.

New or updated information will be recorded in the originally completed eCRF.

The investigator will submit any updated SAE data to sponsor or designee within 24 hours of receipt of the information.

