5.4.2. Adverse Events (AEs)

Adverse Events will be coded using the MedDRA.

An AE is any unfavorable and unintended sign (including a clinically significant abnormal laboratory finding), symptom, or disease (new or exacerbated) temporally associated with the use of study treatment, whether or not considered related to the study treatment. An AE will be considered a treatment emergent adverse event (TEAE) if the AE began or worsened (increased in severity or became serious) on or after the date (and time, if known) of the first administration of study treatment. An AE will be considered a treatment-emergent serious adverse event (TESAE) if it is a TEAE that additionally meets any SAE criterion.

Adverse events will be classified into ocular AEs and non-ocular AEs. An ocular AE will be determined by the location information on the adverse event page in eCRF and thus are not limited to AEs with primary SOCs of eyes. Additionally, questions about adverse event relationships to study treatment and study administration procedure will be asked in eCRF, and the answers to these questions will be used together to derive the treatment related TEAE.

Ocular AEs will be tabulated by treatment cohorts for the study eye and pooled treatment cohorts for the fellow eye, and non-ocular AEs will be summarized by treatment cohorts for participants.

Overall summaries of adverse events will be provided on a per-participant basis by treatment cohorts for categories including the following:

- All TEAEs
- Treatment-related TEAEs
 - Related to study drug
 - Related to study drug administration procedure
- All serious TEAEs
- Treatment-related serious TEAEs
 - Related to study drug
 - Related to study drug administration procedure
- Any TEAE leading to Bimatoprost SR implant removal
- Any TEAE leading to study discontinuation
- Deaths

Any non-ocular TEAEs will be summarized by the primary SOC, PT, and severity including serious TEAEs by the primary SOC and PT, treatment related by SOC and PT and those leading to study discontinuation by the primary SOC and PT.

For incidences of treatment emergent ocular adverse events, summaries will be provided for the following categories:

- Any ocular TEAEs by SOC, PT, and severity
- Any treatment related ocular TEAEs by SOC and PT
- Any serious ocular TEAEs by SOC and PT
- Any ocular TEAEs leading to study discontinuation by SOC and PT
- Any ocular TEAEs resulting in Bimatoprost SR implant removal by PT

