6.3.5. Missing Causal Relationship to Study Intervention for Adverse Events

If the causal relationship to a study treatment is missing for an AE that started on or after the date of the study treatment, a causality of 'yes' will be assigned. The imputed values for causal relationship will be used for the incidence summaries; the values will be shown as missing in the data listings.

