6.3.6. Missing Date Information for Adverse Events

In cases of incomplete dates for AE, the missing component(s) will be assumed as the most conservative value(s) possible. The imputation rule is aimed at conservatively capturing AEs with missing start dates as treatment-emergent AEs (TEAEs).

Table 6-4 **Imputing Rule for Partially Missing AE Start Dates**

Parameter	Missing	Additional Conditions	Imputation
Start date for AEs	D only	M and Y same as M and Y of first dose of study treatment	Date of first dose of study treatment
		Y is before the Y of first dose of study treatment or if Y same but M is before the M of first dose of study treatment	Last day of non-missing month
		Y is after the Y of first dose of study treatment or if Y same but M is after the M of first dose of study treatment	First day of non-missing month
	D and M	Y same as Y of first dose of study treatment	Date of first dose of study treatment
		Y before the Y of first dose of study treatment	Use Dec 31
		Y after the Y of first dose of study treatment	Use Jan 1
	M only	Treat D as missing as well	Use same procedure as D and M missing

Notes: D=Day, M=Month, Y=Year.

If the stop date is complete and the imputed start date computed using the rules in [Table 6-4](#) is after the stop date, the start date will be imputed by the stop date. If the start date is completely missing and the stop date is complete, the following rule will be used to impute the start date:

- If the stop date is after the date of the first dose of study treatment, the date of the first dose of study treatment will be assigned to the missing start date.
- If the stop date is before the date of the first dose of study treatment, the stop date will be assigned to the missing start date.

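### Missing AE severity and relationship are imputed by start date alone, so a pre-dose AE that becomes treatment-emergent by worsening gets the less conservative value

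*SAP*

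**What the plan says.** **Treatment emergence.** SAP 5.4.2 makes an AE a TEAE "if the AE began or worsened (increased in severity or became serious) on or after the date" of first study treatment. Protocol 9.4.2.1 has the same definition. A TEAE that meets any seriousness criterion is a serious TEAE.

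**Missing severity.** SAP 6.3.4 has two branches, both set by start date: "If severity is missing for an AE that started before the date of study treatment, severity of mild will be assigned"; and "If severity is missing for an AE that started on or after the date of study treatment, severity of severe will be assigned". It adds: "The imputed values for severity assessment will be used for the incidence summaries". Listings show the value as missing.

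**Missing relationship.** SAP 6.3.5 has one branch: "If the causal relationship to a study treatment is missing for an AE that started on or after the date of the study treatment", the answer is set to yes. There is no rule for an AE that started earlier.

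**Missing start date.** SAP 6.3.6 says that missing date parts take the most conservative value and that the aim is to capture AEs with missing start dates as TEAEs. Its specific rule for a wholly unknown start date opens with the condition "If the start date is completely missing and the stop date is complete". It then covers a stop date after first dose and a stop date before first dose.

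**Recording of updates.** On AE follow-up, protocol 8.3.3 says: "New or updated information will be recorded in the originally completed eCRF".

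**The concern.** The TEAE definition has two ways in: onset on or after first dose, and worsening on or after first dose. The imputation rules for severity and relationship recognise only the first. An AE that is treatment-emergent by the second route therefore falls in the pre-dose branch, which looks designed for events that do not count as TEAEs at all.

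The consequence runs one way. For these events the severity table would show a milder grade, and the treatment-related tables would omit the event, although the same blank field on a TEAE with post-dose onset would give severe and related. These are pre-existing conditions that got worse after the implant or drops were started, which is a group a safety reader wants treated cautiously.

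A smaller gap sits beside this one. SAP 6.3.6 writes no explicit rule for an AE with a wholly missing start date that is ongoing, has only a partial stop date, or stopped on the day of first dose. Without a start date, 6.3.4 and 6.3.5 cannot be applied either.

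**Working it through.** The plan gives no figure to reproduce. The check applies the written rules of SAP 5.4.2, 6.3.4, 6.3.5 and 6.3.6 to test cases.

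| Case | TEAE? | Severity used | Relationship used |
|---|---|---|---|
| A. Starts pre-dose, serious after dose, both fields missing | Yes, serious TEAE | Mild | Stays missing |
| B. As A, both fields recorded | Yes, serious TEAE | As recorded | As recorded |
| C. Starts after dose, both fields missing | Yes | Severe | Yes |
| D. Starts pre-dose, never worsens, both fields missing | No | Mild | Stays missing |
| E. No start date, stopped after first dose, both fields missing | Yes (start = first dose) | Severe | Yes |
| F. No start date, stopped before first dose, both fields missing | No (start = stop date) | Mild | Stays missing |
| G. No start date, ongoing, both fields missing | No explicit rule | Undefined | Undefined |
| H. No start date, stopped on first-dose date, both fields missing | No explicit rule | Undefined | Undefined |

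A and C have the same missing fields and both are TEAEs, yet they receive opposite treatment. B shows that the mismatch needs a missing field. D and F show that the pre-dose branch does no harm when the AE is not a TEAE.

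**Which events reach case A.** Worsening means increased severity or becoming serious. An increase in severity can hardly be established when severity is blank, so the severity mismatch is essentially confined to a pre-dose AE that became serious. The relationship mismatch is a little wider: it also reaches a pre-dose AE whose severity is recorded as having risen after dosing but whose relationship is blank.

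**Can a pre-dose AE exist in the data?** Protocol 8.3.1 collects AEs from consent. Screening of up to 60 days plus washout of up to 42 days gives 60 + 42 = 102 days before Baseline, so such AEs are plausible. This says nothing about how often fields are missing.

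**Which tables.** SAP 5.4.2 tabulates ocular and non-ocular TEAEs by severity, and treatment-related TEAEs separately. Serious TEAEs are tabulated by SOC and PT, so case A still appears there.

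**Size of one event**, using planned cohort sizes:

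- Bimatoprost SR: 1/30 = 3.3% to 1/25 = 4.0%.
- LUMIGAN 0.01%: 1/5 = 20%.

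These are the weight of any single participant in any table, not an estimate of how many will be affected.

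**The case against.** The strongest reply is that the set of affected events may be empty. Protocol Appendix 3 obliges the investigator to assess relationship for each AE and to do so before an SAE is first transmitted. It also defines intensity grades, and protocol 10.1.6 has monitors verify source data. A serious event with blank severity or relationship should therefore be rare. This stands, with one qualification. Appendix 3 speaks of relationship to study treatment, whereas SAP 5.4.2 derives treatment-related status from two questions, one on the treatment and one on the administration procedure.

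Second, protocol 8.3.3 does not say that a worsened AE keeps its original onset date. Appendix 3 lists exacerbation of a pre-existing condition as meeting the AE definition. If sites enter the exacerbation as a new AE with post-dose onset, 6.3.4 gives severe and 6.3.5 gives yes. This also stands: retention of the early date is an inference, and the documents do not settle it.

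Two stronger readings are tempting and should be resisted. A reader might infer that any pre-dose AE that becomes serious is tabulated as mild. The rules act only on missing values, so it is not. A reader might also infer that an ongoing AE with no start date is denied TEAE status, for instance because a program might treat a missing date as earlier than first dose. The SAP names its software but prescribes no such comparison, and the stated aim of 6.3.6 points to counting the event as a TEAE. These are unstated cases, not exclusions.

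**Conclusion.** The mismatch between SAP 5.4.2 and SAP 6.3.4 and 6.3.5 is real. Followed as written, the rules give a TEAE that qualifies by worsening a less conservative severity, or no imputed relationship, compared with a TEAE that qualifies by onset. This rests on two conditions: the event keeps its pre-dose start date, and severity or relationship is missing. The first is suggested but not stated, and the frequency of the second is not given.

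The effect should be rare and is confined to descriptive safety tables. The event remains a TEAE, and a serious one where applicable, and listings show the field as missing. No efficacy result, sample size or hypothesis is touched. It is worth correcting because the written rule gives the wrong answer for its case, the tables are small, and the correction is a few words. The open cases in 6.3.6 are a minor clarification and would not carry the point alone.

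**What to change.** 1. In SAP 6.3.4, assign severe to missing severity for every TEAE, including pre-dose AEs that became serious or otherwise worsened on or after first dose. Keep mild only for AEs that are not treatment-emergent.
2. In SAP 6.3.5, assign yes to missing relationship for every TEAE, and say that this covers both the study-drug and the administration-procedure questions.
3. To avoid circularity, state that TEAE status is determined from start date, seriousness and any recorded severity before either field is imputed.
4. As a clarification in line with the stated aim of SAP 6.3.6, assign the first-dose date to a wholly missing start date unless the known parts of the stop date show that the AE ended before first dose. This settles ongoing, partial-stop and stop-on-Day-1 events. SAP 6.3.7.2 already writes explicit rules for ongoing and partial stop dates of medications.

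The cost is a few lines of SAP text and a small change to the AE derivation, with no new data collected. The downside is that possibly one or two more events appear as severe, related or treatment-emergent in descriptive tables.

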6.3.5. Missing Causal Relationship to Study Intervention for Adverse Events

If the causal relationship to a study treatment is missing for an AE that started on or after the date of the study treatment, a causality of 'yes' will be assigned. The imputed values for causal relationship will be used for the incidence summaries; the values will be shown as missing in the data listings.

6.3.6. Missing Date Information for Adverse Events

In cases of incomplete dates for AE, the missing component(s) will be assumed as the most conservative value(s) possible. The imputation rule is aimed at conservatively capturing AEs with missing start dates as treatment-emergent AEs (TEAEs).

Table 6-4 **Imputing Rule for Partially Missing AE Start Dates**

Parameter	Missing	Additional Conditions	Imputation
Start date for AEs	D only	M and Y same as M and Y of first dose of study treatment	Date of first dose of study treatment
		Y is before the Y of first dose of study treatment or if Y same but M is before the M of first dose of study treatment	Last day of non-missing month
		Y is after the Y of first dose of study treatment or if Y same but M is after the M of first dose of study treatment	First day of non-missing month
	D and M	Y same as Y of first dose of study treatment	Date of first dose of study treatment
		Y before the Y of first dose of study treatment	Use Dec 31
		Y after the Y of first dose of study treatment	Use Jan 1
	M only	Treat D as missing as well	Use same procedure as D and M missing

Notes: D=Day, M=Month, Y=Year.

If the stop date is complete and the imputed start date computed using the rules in [Table 6-4](#) is after the stop date, the start date will be imputed by the stop date. If the start date is completely missing and the stop date is complete, the following rule will be used to impute the start date:

- If the stop date is after the date of the first dose of study treatment, the date of the first dose of study treatment will be assigned to the missing start date.
- If the stop date is before the date of the first dose of study treatment, the stop date will be assigned to the missing start date.

6.3.7. Missing Date Information for Prior or Concomitant Medications

For prior or concomitant medications, including washout and IOP-lowering medications, incomplete (ie, partly missing) start dates and/or stop dates will be imputed. When the start date and the stop date are both incomplete for a participant, the start date will be imputed first.

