4.2. Full Analysis Set (FAS)

All participants who have received study intervention (ie, Bimatoprost SR administration or LUMIGAN 0.01%) with at least 1 postbaseline IOP assessment (including an unscheduled visit assessment) on the study eye will contribute to the FAS. All efficacy data collected from these participants will be included in the FAS with the following exception:

- To avoid confounding of efficacy data, IOP measurements obtained after initiating the use of non-study rescue IOP-lowering treatment (medication[s] or procedure[s] or both) in an eye will be excluded from FAS.

5. Statistical Analyses

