5.3.4.2. Time-to-Event Analysis

Time to the event of the initial use of nonstudy rescue IOP lowering treatment (medication and/or procedure) in the study eye from the date of Bimatoprost SR treatment will be estimated using Kaplan-Meier (KM) method with graphical display.

Time to initial use of nonstudy rescue IOP lowering treatment = (Date of initial use of non-study IOP-lowering treatment – Date of the Bimatoprost treatment) + 1.

In the calculation of time to initial use of nonstudy rescue IOP lowering treatment, if a participant did not use any nonstudy rescue IOP lowering treatment in the study eye, then the event (initial use of nonstudy rescue IOP lowering treatment) time will be censored at the study exit date or the last visit date if the study exit date is not available.

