6.3.7.1. Incomplete Start Date

The following rules will be applied to impute the missing numeric fields for an incomplete prior or concomitant medication start date. If the stop date is complete (or imputed) and the imputed start date is after the stop date, the start date will be imputed using the stop date.

Table 6-5 **Imputing Rule for Missing Prior or Concomitant Medications Start Date**

Parameter	Missing	Additional Conditions	Imputation
Start date for non-prior or concomitant medications	D only	M and Y same as M and Y of first dose of study treatment	Date of first dose of study treatment
		Y is before the Y of first dose of study treatment or if Y same but M is before the M of first dose of study treatment	Last day of non-missing month
		Y is after the Y of first dose of study treatment or if Y same but M is after the M of first dose of study treatment	First day of non-missing month
	D and M	Y same as Y of first dose of study treatment	Date of first dose of study treatment
		Y before the Y of first dose of study treatment	Use Dec 31
		Y after the Y of first dose of study treatment	Use Jan 1
	M only	Treat D as missing as well	Use same procedure as D and M missing

Notes: D=Day, M=Month, Y=Year.

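### A partial start date for rescue medication is imputed early, by a rule written for concomitant medications. This shortens time to rescue and can remove valid pre-rescue IOP from the FAS.

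*SAP*

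**What the plan says.** The rule in SAP 6.3.7 covers IOP-lowering drugs by name: "For prior or concomitant medications, including washout and IOP-lowering medications, incomplete (ie, partly missing) start dates and/or stop dates will be imputed". SAP 5.3 refers the efficacy analyses to Appendix 3 for data handling, and this rule is part of that appendix.

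Table 6-5 in SAP 6.3.7.1 has four branches that can apply to a treatment started after first dose:

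- Day missing, "M and Y same as M and Y of first dose of study treatment": the first-dose date.
- Day missing, later month: "First day of non-missing month".
- Day and month missing, "Y same as Y of first dose of study treatment": the first-dose date.
- Day and month missing, "Y after the Y of first dose of study treatment": 1 January.

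The only other constraint is an upper one: an imputed start that would fall later than a known or imputed stop is pulled back to that stop.

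Two efficacy steps depend on when rescue began. SAP 4.2 removes from the FAS "IOP measurements obtained after initiating the use of non-study rescue IOP-lowering treatment". SAP 5.3.4.2 calculates time to rescue as "Date of initial use of non-study IOP-lowering treatment" minus the Bimatoprost treatment date, plus 1.

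**The concern.** Dating a drug early is a reasonable default when the question is only whether it counts as concomitant. The start of rescue is different, because it is an efficacy event and also decides which IOP readings are analysed. Table 6-5 can place that start before visits at which the medication review found no rescue. Such a date contradicts data already in hand.

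Two results are exposed. The Kaplan-Meier curve for time to rescue falls too soon. Readings taken before rescue can also be treated as post-rescue and dropped. Protocol 6.5.3 lets rescue start when IOP is not adequately controlled, so the readings just before it tend to be high. Losing them would make the mean IOP change look better than it was.

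**Working it through.** The plan gives no figure for this point, so there is none to reproduce. The check applies Table 6-5 literally.

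**Inputs.** Branches from SAP Table 6-5. Time to rescue = start date − Day 1 date + 1 (SAP 5.3.4.2). Target days from SAP Table 6-1: 2, 56 (Week 8 Sleep Lab), 112, 180, 270 and 360. The Week 8 Office visit is assumed to fall on Day 55. A reading is wrongly dropped if its day is after the imputed start and on or before the true start.

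**Size of the date error.**

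- Day missing: the largest error is a true date on the 31st moved to the 1st, 31 − 1 = 30 days.
- Day and month missing: a true start on Day 360 in the same calendar year as Day 1 becomes Day 1, so 360 − 1 = 359 days.
- No branch moves a post-Day 1 start later, so the error has one sign.

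**Worked dates (illustrative calendar).**

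| Day 1 | True rescue | Missing | Imputed start | Error (days) | Valid readings dropped |
|---|---|---|---|---|---|
| 10 Mar 2020 | 28 May 2020 (Day 80) | day | 1 May (Day 53) | 80 − 53 = 27 | Week 8 Office and Sleep Lab (Days 55, 56) |
| same | same | day, month | 10 Mar (Day 1) | 80 − 1 = 79 | Days 2, 55, 56 |
| 10 Mar 2020 | 28 Aug 2020 (Day 172) | day | 1 Aug (Day 145) | 172 − 145 = 27 | none |
| 15 Sep 2020 | 20 Mar 2021 (Day 187) | day | 1 Mar (Day 168) | 187 − 168 = 19 | Month 6 (Day 180) |
| same | same | day, month | 1 Jan 2021 (Day 109) | 187 − 109 = 78 | Week 16 and Month 6 (Days 112, 180) |

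The third row shows that a missing day need not cost any reading.

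**How often, given that a date is partial.** The rule was run for every true start from Day 2 to Day 360 and every Day 1 date in one calendar year, all weighted equally. The equal weighting is an assumption; the documents say nothing on the distribution.

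- Day missing: mean error 14.3 days; about 21% of cases lose at least one valid reading. If rescue truly starts on Days 57 to 84, 49% lose the Week 8 Sleep Lab profile. If it starts on a scheduled visit day (56, 112, 180 or 270), 97% lose that visit's own reading.
- Day and month missing: mean error 121 days; 51% collapse to Day 1, and about 90% lose at least one valid reading.

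**Weight of one participant.** SAP 3 plans at least 20 evaluable in the Bimatoprost SR cohort from 25 to 30 enrolled. One lost profile removes all 12 primary change values for that participant, which is 1/20 = 5% of the minimum or 1/30 = 3.3% if all 30 are evaluable. One false event at Day 1 lowers the Kaplan-Meier curve by 1/30 = 3.3 points with 30 at risk, or 1/25 = 4 points with 25.

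**The case against.** The strongest reply is that the trigger should be rare. The investigator decides on rescue and attests to the need for it (Protocol 6.5.3). Start and end dates must be recorded (Protocol 6.5), and source data verification is planned (Protocol 10.1.6). A study-visit prescription will usually carry a full date. The study tests no hypothesis, and time to rescue is one of the other efficacy endpoints. All of this stands and limits the weight of the point, but none of it gives the right date when a date is partial.

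A reader might go further and infer three things that the documents do not support.

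- **That any partial rescue date puts the primary endpoint at risk.** Under SAP 5.1 and 5.5 the primary and secondary results come from the first lock and are treated as final. Rescue recorded after that lock cannot remove Week 8 data from them. Where rescue truly began before the Week 8 Sleep Lab visit, the plan excludes that profile anyway. The exposure is therefore to rescue begun after Week 8 and recorded before the first lock, chiefly in early enrollees.
- **That the reading which prompted rescue is always deleted.** With only the day missing, that reading must fall in the same calendar month as rescue and after the 1st. Protocol 6.5.3 asks for confirmation on another day, so the prompting reading may lie in an earlier month. A confirming reading may be unscheduled, and SAP 6.3.1 already leaves those out of efficacy unless no other value is in the window.
- **That the rule favours the product throughout.** On time to rescue an early date is unfavourable. Only the loss of high pre-rescue readings works the other way.

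**Conclusion.** The defect is real but narrow. Whenever a rescue-medication start date is partial, the stated rule gives a date that is at or before the true one and may contradict a visit already recorded as free of rescue. Time to rescue is too short by 0 to 30 days with the day missing, and by up to about 359 days with day and month missing. Valid IOP is lost only when a reading lies between the two dates. Harm to the primary analysis is confined to rescue recorded before the first lock; otherwise the effect is on the Hour 0 summaries and the Kaplan-Meier estimate.

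The direction and the maxima follow from Table 6-5, taking rescue by Day 360. The percentages depend on the assumed uniform dates and visit days and apply only to participants with a partial date. The documents give no rate of partial dates, so the expected number affected cannot be calculated; it should be small.

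There is also a gap. SAP 4.2 and 5.3.4.2 count rescue procedures as well as medications, but SAP 6.3.7 covers medications only, so a partial procedure date has no rule at all.

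**What to change.** Add one paragraph to the SAP before the first database lock:

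1. For the FAS exclusion and the Kaplan-Meier analysis, exempt nonstudy IOP-lowering treatment in the study eye, both medications and procedures, from Table 6-5.
2. Query any partial start date. If it stays partial, use the later of the Table 6-5 date and the day after the last visit whose medication and procedure review recorded no rescue. Use the same date in both analyses.
3. State that IOP measured at the visit where rescue is first started counts as pre-rescue and is kept.
4. Flag imputed rescue dates in a listing.

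In the first worked case the last rescue-free visit is 4 May (Day 56), so the start becomes 5 May (Day 57) whichever parts are missing. The Week 8 readings stay, and the error is 80 − 57 = 23 days instead of 27 or 79.

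Item 3 is needed because item 2 alone does not protect the visit where rescue begins. With Day 1 on 10 March 2020 and rescue started at Week 16 on 29 June (Day 112), a missing day still gives 1 June (Day 84), since the last rescue-free visit is Week 8. Item 3 keeps the Week 16 reading, although time to rescue remains 112 − 84 = 28 days short.

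If the review is accurate, the new date is still no later than the true start, so no post-rescue reading is readmitted. The schedule of activities already collects medications and procedures at each contact, so no new data are needed. The cost is the paragraph itself and dependence on the accuracy of that review.
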